Research in a range of occupational settings has indicated that resilience plays an important role in ameliorating the impact of adverse events in high pressure environments. This project will use a randomised controlled trial research design to assess the efficacy of brief one-to-one Acceptance and Commitment Training (ACTr), designed to enhance surgeons' psychological resilience. According to acceptance and commitment therapy (Hayes, 2004), psychological flexibility is implicated in psychopathology. Psychopathology is primarily the consequence of psychological inflexibility i.e. inability to persist or change behaviour according to long-term values due to language and cognition skills (Hayes, 2006), which has particular significance when an individual is confronted with stress or adversity.

2: Aims and Objectives

The main aim of our research is to assess the efficacy of a brief Acceptance and Commitment Training course. We wish to ascertain whether such a course can increase surgeons' resilience by increasing psychological flexibility, valuing and self-compassion (all of which are expected to be positively impacted by this training). This research will fill a gap in the relevant research literature; namely that no research project as far as we are aware has evaluated ACTr as a means to enhance resilience in surgeons. In fact any research conducted on resilience training with a surgical population is rare.

3: Design

The proposed study will initially take the shape of a small pilot study (n=10) and following this a randomised controlled trial. (n=100)

The intervention will consist of Acceptance and Commitment Training (ACTr), on a 1:1 basis. Flaxman (2013) devised a workplace training program which will form the basis of this training protocol. ACT as a workplace training has been supported by numerous studies including Lappalainen et al (2007), Finnes and Ghaderi (2017). A recent manual, Flaxman, Bond and Livheim (2013), will be utilised for this study, with a bespoke tailoring to the surgeons' population. See section 12 for full details.

4: Participants

Trainee surgeons and consultant surgeons from local hospitals, initially Royal Bournemouth Hospital, Bournemouth, Dorset; and Poole Hospital, Poole, Dorset. Then the John Radcliffe Hospital, Oxford; Southampton General Hospital, Southampton and Portsmouth General Hospital.

5: Sampling

Strategy

Block randomisation (blocks of 4) will be used to help ensure equal-sized groups. An external statistician will generate random blocks of 4.

Sample Size

For the RCT, we intend to recruit 100 to allow for some attrition and still have approximately 45 participants per condition. This number is based on previous studies(e.g Flaxman and Bond, 2010) conducted using ACTr based training; this will give enough statistical power, particularly with regards to mediation analysis.

6: Recruitment

Recruitment will initially be through Royal Bournemouth Hospital and will be initiated by [name], MA DM FRCS(Urol) (Principal Investigator). An invitation email will be sent to potential participants (again identified by [name]) and further information regarding the study will be forwarded to the potential participant on their request only.

7: Randomisation

Participants will be allocated one of two groups, the experimental group (who will receive ACTr) or the wait-list control group. Participants allocated to the wait-list control will be offered the same ACTr sessions once the current study has ended.

8: Data Collection

Data Collection Points

T1 – 2 Weeks before training session one. Via email/on-line questionnaires.

S1- First training session

Interval (4 weeks RCT, 2 weeks Pilot)

T2 – Immediately before the beginning of training session two.

S2 – Second Training session

Interval (4 weeks RCT, 2 weeks Pilot)

T3 - Immediately before the beginning of training session three.

S3 – Third Training session

T4 –Within two week of completion of training session three.

T5- Follow-up, 12 weeks after training session three. Via email.

Primary Outcome Measures

Resilience - Brief Resilience Scale (BRS)

General Health - General Health Questionnaire (GHQ-12)

Secondary Outcome and Process Measures

CBI (Copenhagen Burnout Inventory)

DASS21 (Depression Anxiety and Stress Scale)

VLQ (Value Living Questionnaire)

WAAQ (Work related Acceptance and Action Questionnaire)

AAQII (Acceptance and Action Questionnaire)

SCS (Self Compassion Scale)

SPS (Sense of Preparedness Scale)

9: Data Analysis

[figure not shown]
Data will be analysed on an intention-to-treat basis. For the pilot study a series of analyses of variance with time (1-5) as a within-subjects factor will be employed to examine changes in outcome and process measures. For the RCT, a series of analyses of variance will be conducted with time(1-5) as a within-subjects factor and condition (treatment vs control) as a between-subjects factor.

Mediation analysis based on regression will be used to test the role of study processes to ascertain whether outcome measure changes are mediated by process measures.

Furthermore the Jacobson and Truax (1991) method of assessing change for each individual participant will be used in both the pilot and the RCT studies. This will be used to determine whether the magnitude of change for a given client is statistically reliable.

CONSORT 2010 Flow Diagram

Data collected will be presented and analysed descriptively. The consort flow diagram (2010, figure 1.) will be followed to document relevant recruitment data.

Figure 1 (Consort 2010 Flow Diagram)

10: Ethical Considerations

Ethical approval will be sought from the university ethics team and the Integrated Research Application System (IRAS). The researcher will undertake 'Good Clinical Practice' training. Informed consent will be gained at the time of recruitment and verbally prior to the start of each session. Participants will be made aware of their right to withdraw at any time. In the highly unlikely event that participants experience an unexpected uncomfortable response during the session, emotional 'grounding techniques' will be utilised by the trainer. Furthermore, Clinical Psychologist [name] (Chief Investigator) contact details will be made available to participants, as will details of the BMA's Doctors for Doctors website and helpline (who can offer ongoing counselling).

11: Data Protection and Storage

Recordings

Training sessions will be recorded as a further safeguard and assessment tool. The only purpose of recording the sessions is to ensure the ACTr process is being delivered accurately and correctly. Randomly selected section of sessions will be assessed by an independent ACTr assessor ([name] will source the assessor and this will be kept on file) to rate fidelity to the established ACTr protocol. If, a randomly selected recording identifies the participant or anyone else, it will NOT be forwarded to the independent assessor, and another recording will be randomly selected.

Data

All information will be kept on a secure university hard drive. All data will be password protected. All data will be identified only by participant number. An Excel file linking participant to participant number will be kept on a separate drive, on a separate computer, password protected. Paperwork will be kept in a locked filing cabinet in a locked office at Bournemouth University,. Computers are both password secure and encrypted. NO personal information will be kept on laptop computers.

Confidentiality

The NHS code of confidentiality will be adhered to. Both [name] and [name] are both NHS employees and as such have been trained within the last 12 months in Information Governance and Confidentiality. Bournemouth University staff will adhere to the requirements of the Data Protection Act. Furthermore, Access to personal data will be limited to the research team. All data will be anonymised at the earliest possible stage. Personal information will not be kept once participants have completed their 3-month follow-up session. Participants may withdraw at any time and all personal data will be destroyed if this is the case.

12: Training Protocol with example timings.

Training Session 1

- *Develop a rapport with individuals and create a climate of safety and warmth.*
- *Describe the basic format, content and aim of the training.*
- *Install hope that training has the potential to be unusual, interesting and effective*
- *Range of empirically supported ACT exercises as per Flaxman, Bond and Livheim (2014) such as those outlined below*

Day 1	Phase	Intervention	Detail
9.00	Welcome and Introduction	Mindfulness or values warm-up exercise	Re-consent Recording sessions - rationale Designed to build rapport, engage and be 'ACT' consistent. To gather hopes and expectations for the training. Introductions

			
– name, work details, 2 activities they do on automatic pilot and 2 activities they perform with more psychological awareness
 
We teach ACT skills experientially as well as didactically so there'll be a mix of information sharing, skills practices, discussion, goal setting etc.
 
Confidentiality: It's not therapy but it is personal.
 
What do you hope to get out of it personally?
 
Important to attend every session
 
It's a psychological and behavioural skills training program – training - not therapy
 
Research evidence
 
Training is not limited to work-related resilience and wellbeing – the skills can be applied to all areas of life
 
Practicing skills between sessions is an essential part of the training

--	--	--	---

9.20	Overview of the training	Presentation of two skills organising diagram.	
To offer empirical evidence for both ACT in occupational settings and for particular processes or components - e.g. mindfulness
 
Two broad related skills: mindfulness and values-based action
 
The diagram is basically an overview of the entire training
 
More about mindfulness and values-based action
 
Mindfulness evidence base – can be used to enhance resilience in people who are already fairly resilient, and can also be used to reduce stress, burnout, depression and so on, when people are going through challenging times
 
Values-based action – goal setting with a difference
 
Together they can also help when we're experiencing loss of purpose in life, self-doubt, increase effectiveness and performance

9.35	Introduction to mindfulness	
Raisin exercise
 
Brief mindfulness of body and breath.
	
Rest of the session – an introduction to the two main skills
 
Present-moment awareness training
 
Widely recognized effective introduction to mindfulness (Kabat-Zinn 1990). Aid recognition of the experiential distinction between automatic-pilot and present moment awareness.

9.50	Break		
10.00	Introduction to Values-Based Action	Values card sort.	
(I) Provide practical definition of values from ACT perspective. Show potential benefits of guiding daily behaviour through personally chosen values. (ii) Encourage participant to choose one value for one life domain and translate into a series of specific actions (for next session). (iii) Help participant anticipate the thoughts and feelings that may function as internal barriers to valued behavioural activation.

10.20	Introduction to Values-Based Action (continued)	Compass metaphor.	Activate nature of valuing (Hayes et al. 1999). Using the metaphor to illustrate the distinctions between values, value-based goals and value based actions and to illustrate that values are not 'in the future' but available as a potential guide to action in each and every moment.
10.30	Presentation of rationale for the program	Two sheets of paper technique.	One sheet has word 'VALUE' written on it, the other "'UNHELPFUL" THOUGHT/FEELING/MOOD' Geared towards helping client make personal values a more prominent guide to daily actions and life goals.

10.40	Discussion of home practice assignments	Home practice handouts; Environmental reminders: Coaching around effective goals setting – worksheet 3 valued based actions 10-minute mindfulness of breath	
Define one value and translate into specific actions for the next session. To notice what it is like deliberately taking actions that are guided by personal values. To become aware of any internal barriers that actually (or almost) interfere with value-directed action.
 
Reminder that participant can make contact between sessions if there are any concerns or queries

Training Session 2

(4 weeks after session 1; 2 weeks for pilot)

- **Reduce excessive entanglement with unhelpful thought content.**
- **Undermine experiential avoidance.**
- **Cultivate acceptance skills.**
- **Range of empirically supported ACT exercises as per Flaxman, Bond and Livheim (2014) such as those outlined below**

Day 2	Phase	Intervention	Detail
8.45	Data Collection	Collect Data	
9.00	Opening mindfulness	Mindfulness of breath; noticing thoughts and	Involves participant sitting in upright position, eyes closed of unfocused and cast down towards floor, hands resting

	practice and brief review	feelings and allowing them to come and go.	comfortably on lap or arms of chair. Participant will be invited to become aware of physical sensations before setting attention on sensation of movement in the abdomen whilst breathing.
9.10	Home practice review	Discussion	Clarify understanding of the key feature of mindfulness and value-based action processes. Emphasise the importance of generalising mindfulness and value-based action from the session to daily life. Provide reinforcement to participants who have engaged in mindful and value-based action exercises outside the training. Getting clues about barriers – what got in the way if homework was difficult to complete,
9.20	Presentation of training rationale	Passengers on the bus metaphor.	ACT metaphor found in numerous ACT texts (Hayes et al. 1999). Used to portray the functional link between mindfulness and value-based action. Illustrates person driving bus to some extent distinct from own thought and feelings. Some passengers (thoughts/feelings) can be unhelpful and exert subtle/not so

			
subtle) influence over driver's actions. Removing passengers may not be helpful.
 
A lot of unpacking – it's a key learning from the training – your thoughts/memories/emotions/bodily sensations/urges can all be saying do one thing and you can choose to do another, because it's in the service of your value

9.40	Untangling from thought barriers to valued action	
Hand in the face metaphor
 
Old film metaphor
 
Self-reflection on unhelpful thought content
 
Thoughts on screen exercise.
 
2 of 4 options?
	
Cognitive Defusion. Defusion exercises train people to take unhelpful thoughts a bit less seriously; notice the ongoing process of thinking; and learn experientially that thoughts do not have to control action (Harris, 2009). ACT's defusion strategies focus primarily on helping participants relate differently to thoughts that interfere with valued action.

9.55	Break		
10.05	Mindfulness of mood/emotion	
Brief mindfulness of stressful event or
	
Enhancing the participant experiential acceptance skills. Defusion and acceptance are related processes within the ACT model.

		
thought – locating in the body
 
Physicalizing exercise
	
And it is useful to organise them under the same theme of noticing and untangling from internal barriers to valued action.
 
This in turn feeds into the broader purpose of gradually increasing the prominence of people's personally chosen values as a guide to goals and daily action (Flaxman et al., 2013)

10.25	Defining values and value-based goal and action planning	
Construction of four-week values-based goal plan and action plan.
	
Define values in at least two areas of life (preferably different areas as defined on Day 1. Set suitable specific short-term, medium term and long term goals that would help to bring one or two values to life. Participants will be encouraged to set 4 short-term value based goals they are motivated to achieve in next 4 weeks.

	Discussion of home practice assignments	
Home practice handout; environmental reminders; public commitment to one value -based goal
	
Participants are invited to engage mindfully in three value-based actions over the next weeks. These values should be selected by the participant from those identified in the previous /Defining values' exercise.
 
Think about continuing mindfulness practice homework – doing every day activities mindfully – brushing teeth, walking from car to hospital etc.

			Reminder that participant can make contact between sessions if there are any concerns or queries
--	--	--	--

Training Session 3

(4 weeks after session 2 for RCT, 2 weeks for pilot)

- **Booster Session.**
- **Further rehearsal of exercises; basic mindfulness training, physicalizing exercise, diffusion, mindfulness of thought, value-based goal and action planning.**
- **Range of empirically supported ACT exercises as per Flaxman, Bond and Livheim (2014) such as those outlined below.**

Day 3	Phase	Intervention	Process/Reason/function
8.45	Data Collection	Collection of Data	
9.00	Welcome Back	Two-skills diagram.	Welcome back to part three and to reaffirm the empirical evidence for both ACT in occupational settings and for particular processes or components - e.g. mindfulness Also, any evidence to do with medical professional in particular
9.10	Opening	Mindfulness of body	Preparation involves participant sitting in upright position, eyes

	mindfulness practice	and breath.	
closed or unfocused and cast down towards floor, hands resting comfortably on lap or arms of chair. Participant will be invited to become aware of physical sensations before setting attention on sensation of movement in the abdomen whilst breathing.
 
Function of starting with a mindfulness practice:
 
Bring attention into the room and the present moment
 
More likely to be fully engaged in later exercises if do mindfulness practice now
 
Brief inquiry after the practice

9.20	Home practice review	Discussion	
Clarify understanding of the key feature of mindfulness and value-based action processes. Emphasise the importance of generalising mindfulness and value-based action from the session to daily life. Provide reinforcement to participants who have engaged in mindful and value-based action exercises outside the training.

9.35	Assessing value consistency	Self-reflection on value-consistent and inconsistent actions	
An important part of values work involves asking participants to reflect on the value consistency or inconsistency of their recent patterns of behaviour. Participants asked to rate both the

		over past 2 weeks.	importance they attach to a particular value in their life at this moment in time and effective, successful or consistent they had been at pursuing this value over the last few weeks (Wilson et al., 2010). Any high discrepancy between value importance and value consistency may indicate a particular value of life is that is being neglected. VLQ? Bull's-eye?
9.50	Mindfulness of thought and feeling	Thoughts on clouds exercise, contacting the resilient 'observer' perspective.	Reaffirm and enhance the participant experiential acceptance skills. Defusion and acceptance are related processes within the ACT model. And it is useful to organise them under the same theme of noticing and untangling from internal barriers to valued action. This in turn feeds into the broader purpose of gradually increasing the prominence of people's personally chosen values as a guide to goals and daily action (Flaxman et al., 2013) Observer self: and who is it who's doing the noticing? Dream metaphor Hierarchical relationship between observer self and content of experience rather than just a separate relationship Reflection on these practices – their uses and implications

10.10	Break		
10.20	Values-based goal and action planning	Short-term, medium term and long term values-based goal-setting exercise; values-based action map	Define values in at least two areas of life (preferably different areas as defined on Day 1. Set suitable specific short-term, medium term and long term goals that would help to bring one or two values to life. Again, participants will be encouraged to set 4 short-term value based goals they are motivated to achieve in next 4 weeks.
10.30	Recommendation for continued practice	Home practice handout; top tips for building a valued life.	Handout for home practice. Tips for future practice after this final session.
10.40	Final personal reflections on the training	Discussion	Discuss with participant the three training days, assessment of course delivery, potential for improvements. Reminder that participant can make contact post training if there are any concerns or queries

13: Timelines

2017-2018	Sept	Oct	Nov	Dec	Jan	Feb	Mar	Apr	May	June	July	Aug
Training and Data Collection												

2018-2019	Sept	Oct	Nov	Dec	Jan	Feb	Mar	Apr	May	June	July	Aug
Training and Data Collection												
Write Up												

14: References

Hayes, S. C., Luoma, J. B., Bond, F. W., Masuda, A., & Lillis, J. (2006). Acceptance and Commitment Therapy: Model, processes, and outcomes. *Behaviour Research and Therapy*, 44(1), 1-25.

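### The stated randomisation balances only arm size, and career grade (trainee or consultant) is controlled in neither the stated allocation nor the stated ANOVA

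*Protocol*

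**What the plan says.** The allocation method is described only in Protocol section 5 (Sampling): "Block randomisation (blocks of 4) will be used to help ensure equal-sized groups", followed by "An external statistician will generate random blocks of 4". Equal arm size is the only purpose given. Section 7 (Randomisation) adds the two arms: "Participants will be allocated one of two groups, the experimental group (who will receive ACTr) or the wait-list control group". Neither section mentions stratification, minimisation or separate lists.

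Section 4 (Participants) defines a population of two career grades: "Trainee surgeons and consultant surgeons from local hospitals, initially Royal Bournemouth Hospital, Bournemouth, Dorset; and Poole Hospital, Poole, Dorset". Three further hospitals follow later: "Then the John Radcliffe Hospital, Oxford; Southampton General Hospital, Southampton and Portsmouth General Hospital".

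On numbers, section 5 says "we intend to recruit 100 to allow for some attrition and still have approximately 45 participants per condition". For the RCT, section 9 (Data Analysis) specifies analyses of variance with time as the within-subjects factor and condition as the between-subjects factor. Grade does not appear in that model.

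**The concern.** Blocks of 4 that mix trainees and consultants equalise the arm totals but do not control how many trainees each arm receives. Grade is known at recruitment and is the most obvious division in the population as section 4 describes it.

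The outcomes are self-reported resilience, general health, burnout, stress and related processes. From T1 to T5 they are followed for 2 + 4 + 4 + 12 = 22 weeks (section 8). It is plausible, though the protocol does not say so, that these measures take different courses in trainees and consultants over that time. A stable grade difference cancels when each person is compared with their own T1 score. A grade difference in change does not cancel, and an uneven trainee split would carry part of it into the arm contrast of this one trial. A visible imbalance on grade would also be awkward to explain when the result is reported.

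**Working it through.** **Inputs from the protocol.** 100 recruited; two arms intended to be equal, so 50 per arm; blocks of 4 (100/4 = 25 complete blocks); about 45 per arm retained. The two sample-size figures agree with each other: 2 × 45 = 90, and 90/0.90 = 100, an implied attrition of 10%.

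**Assumed inputs, because the protocol gives none.** Trainee share 50%, with 30% as a second case. Grade effect on outcome change 0.2 to 0.5 SD. Trainees and consultants enter in random order.

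**Step 1: chance imbalance under the stated scheme.** With 25 complete blocks and random order of entry, the number of trainees K in one arm is hypergeometric: 50 drawn from 100, of whom T are trainees.

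- The between-arm gap in trainee share is 2(K − T/2)/50, so each trainee above or below the expected number is worth 4 points.
- A gap of 12 points or more means K is at least 3 from its expectation. A gap of 20 or more means at least 5.
- For T = 50: SD(K) = √(50 × 0.5 × 0.5 × 50/99) = 2.51, so the SD of the gap is 2 × 2.51/50 = 10 points.
- For T = 30: SD(K) = √(50 × 0.3 × 0.7 × 50/99) = 2.30, so the SD of the gap is 9 points.

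| Trainees among 100 (assumed) | SD of gap | Gap ≥ 12 points | Gap ≥ 20 points |
|---|---|---|---|
| 50 | 10 points | 31.7% | 7.1% |
| 30 | 9 points | 27.5% | 4.9% |

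A Monte Carlo run of 40,000 trials with 50 trainees gave 31.8% and 7.1%.

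**Step 2: effect on the result.** Shift in the arm contrast = gap × grade effect.

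- 12-point gap: 0.12 × 0.2 = 0.024 SD to 0.12 × 0.5 = 0.06 SD.
- 20-point gap: 0.20 × 0.2 = 0.04 SD to 0.20 × 0.5 = 0.10 SD.

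The standard error of the arm difference at 45 per arm is √(2/45) = 0.21 SD. Even the larger shift is under half a standard error (0.10/0.21 = 0.47).

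**Step 3: precision to be gained.** With half trainees, grade explains a variance of 0.5 × 0.5 × d², for a grade effect d in units of the total SD.

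- d = 0.2: 0.01 of the variance; the standard error falls by 1 − √0.99 = 0.5%.
- d = 0.5: 0.0625 of the variance; it falls by 1 − √0.9375 = 3.2%.

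**Step 4: with two lists by grade.** An unfinished block of 4 can leave a list out of balance by at most 2, so the trainee count differs between arms by at most 2. In simulation (20,000 trials; 30% or 50% trainees) the SD of the gap fell from 9 to 10 points to about 1.3 to 1.4 points, and the chance of a gap of 10 points or more fell from about 33 to 37% to essentially nil. Arm totals can differ by at most 2 + 2 = 4.

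**The case against.** The case for leaving the plan alone has four parts, and much of it stands.

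- **Blocks of 4 achieve their stated aim, and a single list is only inferred.** Both are true. The protocol never says that there is one list, so the accurate statement is that no stratification is stated. The statistical analysis plan, which is not at hand, could add grade to the model. It could not restore stratification once the list has been generated, so the allocation half of the point belongs to the protocol.
- **Chance imbalance is already part of the randomised test.** This stands. A reader might infer that an uneven trainee split biases the treatment effect or makes the test invalid. It does neither: over repeated randomisations the comparison is unbiased, and its standard error already allows for such imbalance.
- **The effect is small.** This also stands. The shift is a fraction of one standard error, and adjustment for grade alone, without a second list, would recover nearly all the precision.
- **Hospital.** A reader might extend the point to the five hospitals and conclude that they too need stratifying. The documents do not support that. Section 4 describes two hospitals initially and three afterwards, and section 6 starts recruitment at one of them. Consecutive blocks then already limit hospital imbalance in part, and almost wholly if hospitals recruit strictly one after another. Large hospital imbalances become common only if all five are assumed to recruit at once, which the protocol does not describe. Phasing gives grade no such protection.

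**Conclusion.** The point holds for grade, as a low-priority improvement. The protocol enrols two career grades and controls grade in neither the allocation nor the analysis that it states. On the assumption of equal numbers of trainees and consultants, about one trial in three would show a gap of 12 points or more in trainee share, and about one in fourteen a gap of 20 or more. The trial remains valid and unbiased. What is lost is some credibility and, on the assumed grade effects, 0.5% to 3% in the standard error. The grade mix and the size of the grade effect are both assumptions; a weaker grade effect would make the point smaller still.

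**What to change.** Before the allocation sequence is generated, amend section 5 so that the external statistician prepares separate permuted-block lists for trainees and for consultants. In section 9, add grade as a factor in the condition comparison. Hospital need not be a stratifier, though it may be added as a model factor. Crossing grade with five hospitals would create ten small strata; in simulation with 20 participants per hospital, that let arm totals drift apart by up to 12.

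The cost is one extra list from a statistician already engaged and one degree of freedom for grade. Arm totals may differ by up to 4, instead of the 2 possible if recruitment stops partway through a block under the present scheme.

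### Section 5 fixes and states a single block size of 4; if surgeons are allocated singly and recruiters know the earlier arms, up to one third of allocations on average are certain in advance

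*Protocol*

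**What the plan says.** Section 5 (Sampling, Strategy) gives the block size twice: "Block randomisation (blocks of 4) will be used to help ensure equal-sized groups", and then "An external statistician will generate random blocks of 4". It mentions no variation in size. The only purpose given for blocking is balance between the arms.

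Section 5 (Sample Size) sets the number: "we intend to recruit 100 to allow for some attrition and still have approximately 45 participants per condition".

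Section 6 has the principal investigator start recruitment, initially through one hospital, and choose whom to approach: "An invitation email will be sent to potential participants (again identified by" that investigator). Further information goes only to those who ask for it.

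Section 7 describes the arms: "Participants will be allocated one of two groups, the experimental group (who will receive ACTr) or the wait-list control group". Wait-list surgeons are offered the sessions after the study ends.

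Section 9 plans "a series of analyses of variance will be conducted with time(1-5) as a within-subjects factor and condition (treatment vs control) as a between-subjects factor".

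The protocol does not say whether surgeons are allocated singly or in batches, or who learns of an allocation once it is made.

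**The concern.** With a fixed block size that the investigators know, the end of each block can be worked out from the arms already assigned. Having an outside statistician generate the list protects how it is made. It does not stop this deduction when the size is known and the arms are visible. Here they become visible, because one arm is trained during the study and the other is not.

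A person who can foresee the next arm and also influences who is approached, or when, can let the choice of surgeon follow the arm, even without intending to. The two groups would then no longer be comparable by design. The planned analysis gives partial protection. T1 is one of the time points, so a stable difference in level between the arms drops out of the time-by-condition interaction. Differing trajectories, or regression to the mean after selection on a passing state, would not drop out.

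**Working it through.** **Inputs.** The block size of 4 and the two arms come from sections 5 and 7. The 2 + 2 split within a block is inferred from the stated aim of equal groups, since no ratio is given. The total of 100 comes from section 5 and makes 100/4 = 25 blocks on one list, as no stratification is stated. The protocol gives no predictability figure of its own to reproduce.

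**Step 1: fixed blocks of 4, single allocation, all earlier arms known.** There are 6 equally likely orderings of AABB. An allocation is certain when one arm's two places are already used.

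- AABB and BBAA: places 3 and 4 are certain, 2 each.
- The other four orderings: only place 4 is certain, 1 each.
- Mean per block = (2×2 + 4×1)/6 = 8/6 = 4/3. Share = (4/3)/4 = 8/24 = 33.3%.
- Best guess (always naming the arm with more places left): right with probability 1/2, 2/3, 2/3 and 1 at places 1 to 4. Mean = (17/6)/4 = 17/24 = 70.8%, against 50% by chance.
- Over 25 blocks the certain count is 25 + Binomial(25, 1/3): mean 33.3, possible range 25 to 50, 5th to 95th percentile 30 to 37.

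**Step 2: partial knowledge.** Assume that each allocation is seen independently with probability q and that the observer still knows the place in the block. Place 3 is certain if places 1 and 2 match (1/3) and both were seen: q²/3. Among the first three places one arm always appears twice; place 4 is certain if both of those were seen: q². Share = (q²/3 + q²)/4 = q²/3.

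| q (assumed) | Certain in advance | Best guess right |
|---|---|---|
| 1 | 33.3% | 70.8% |
| 0.75 | 0.5625/3 = 18.8% | 64.6% |
| 0.5 | 0.25/3 = 8.3% | 59.9% |
| 0.25 | 0.0625/3 = 2.1% | 55.4% |

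If a whole block is enrolled before any of its allocations is released, the share is 0.

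**Step 3: varying sizes.** This was simulated on lists of 100, sizes equally likely, with an observer who knows all earlier arms and has also guessed the set of sizes.

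| Sizes | Certain in advance | Best guess right |
|---|---|---|
| 4, 6, 8 | about 2.4% (2.1% to 2.4% between runs) | 67.9% |
| 4, 6 | 5.6% | 69.2% |
| 2, 4, 6 | 4.0% | 70.1% |

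At q = 0.5, sizes 4, 6 and 8 give under 0.1% certain and a best guess of 57.8%.

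**Step 4: effect on balance.** With exactly 100 enrolled on one list, fixed blocks of 4 give 50:50 every time. Sizes 4, 6 and 8 give arms differing by 0.54 on average and by at most 4; about 73% of lists are exactly balanced. If 98 enrol, the mean difference is 0.66 with fixed blocks and 0.56 with varying ones.

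**The case against.** The strongest reply is that the harm depends on conditions the protocol does not state. If the list is properly concealed, or surgeons are allocated in complete blocks, a known block size gives away little or nothing. These arrangements are often set out in separate trial procedures, so silence here does not show that they are absent. That stands, and it makes one third a ceiling.

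Full knowledge of earlier arms is also harder to obtain than section 6 alone suggests. Section 4 names two initial hospitals and three later ones, so on one list a recruiter would need to see allocations at every active site. Steering is weak too. Invitations go to several surgeons, who decide whether and when to reply, so the order of invitation need not match the order of allocation. Both points stand.

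A reader might want to turn predictability into a bias in standard deviations, by supposing that surgeons are selected on their T1 score. The documents do not support this. T1 is collected two weeks before the first session, and nothing shows that it exists when a surgeon is invited. A reader might also infer that the block size was public during recruitment. The documents do not show when the protocol was released; they show only that the size stands in the protocol.

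Last, the remedy lowers best-guess success by only about 3 percentage points and gives up guaranteed exact balance. Both are true. What it removes is certainty, and the loss of balance is slight.

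**Conclusion.** The point holds in a limited form. The protocol itself makes and discloses the choice of one fixed block size, so this is not a detail left to a later plan. The share of allocations certain in advance lies between 0 and 33.3% on average. The upper end requires single sequential allocation, full knowledge of earlier arms and 2 + 2 blocks.

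It would be wrong to read this as saying that a third of this trial's allocations were or will be foreseen, or that allocation was not concealed. The document shows neither. Any resulting bias is likely to be small and cannot be quantified from the protocol.

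Severity: consider, as a cheap improvement.

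**What to change.** In section 5, replace the fixed size with a statement that the external statistician will use randomly varying block sizes, with the sizes recorded in a document withheld from those who recruit. Remove the figure 4 from both sentences. Sizes 4, 6 and 8 are a reasonable example and leave fewer certain places than 4 and 6 or 2, 4 and 6.

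Concealment of the list is still needed, because varying the sizes leaves best-guess success at about 68% for an observer who sees every earlier arm.

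The cost is a short edit to section 5 and a new list from the same statistician. The downside is the small loss of balance shown above, which is minor against a target of about 45 completers per arm.
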